### 2.8. Voluntary Participation/Right to Refuse or Withdraw

There is no obligation for participants to be involved in this study. If participants decide to participate in the study and later feel they no longer wish to be part of it, participants may withdraw from the study at any time without prejudice to any current or future involvement in clinical studies held by the study investigators or sponsor. If participants withdraw their consent, all data collected up until that time will be used in the analysis of the data.

All communications will be performed by a trained iwi Qualitas employee (Study Director) or the Principal Investigator [name]. In the event that [name] does not screen the participant, [name] will review case files before participants are enrolled. Any participant that presents a response

4-Mar-2022

or result (e.g., blood test) that is outside of normal range will be directed by ImawareTM to medically trained professionals with their results.

### 2.9. Patient disposition, disease history and medical history

### 2.9.1. Basic health and background data

Health and baseline disease characteristics data, as characterized by the questionnaire will be summarized and listed. Categorical data, (e.g., gender, smoking, level of physical activity, medication use, etc.) will be summarized and the percentage of participants who answer "yes" to the set questions will be calculated. Continuous data, e.g., age, weight, height, body mass index, will be summarized by descriptive statistics (N, mean, median, standard deviation, minimum and maximum). BMI (kg/m2) will be calculated as weight[kg] / (height[m]2) using weight at Baseline.

### 2.9.2. Diagnosis and Family disease history

Diagnosis of Cardiovascular disease and Diabetes, as well as family history of cardiovascular disease and Diabetes will be documented as categorical data. The percentage of participants with cardiovascular disease, diabetes and family history of the diseases will be calculated as well.

### 2.10. Termination of the Study

This research project may be stopped for a variety of reasons.

During the trial, any participant that records out-of-range analytical levels will be referred to their GP for assessment of suitability/safety for continuation in the trial.

At the discretion of the GP the participant will either be placed on standard care of cholesterol-lowering medication (and removed from the trial) or continue in the trial on the supplementation.

The participant also has the option to stop supplementation at any point.

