### Confidential

### 4-Mar-2022

| Table 1-1
Table 2-1
Table 2-2  | Study design  Treatment Plan  Laboratory parameters to be investigated by Imaware   | 7 |
|--|---|---|
| List of figure 1-1   | res
Study design   | 5 |
| List of abb  | reviations  |   |
| AE CSP CSR FAS GCP GLU HbA1c HDL Hs-CRP ITT LDL N N/A Non-HDL-C PP SAE TC TC: HDL TG | Adverse Event Clinical Study Protocol Clinical study report Full Analysis Set Good Clinical Practice Glucose Glycated hemoglobin High-Density Lipoprotein High sensitivity C-reactive Protein Intention-To-Treat Population Low-density Lipoprotein Sample size Not applicable Non-High-density lipoprotein cholesterol Per protocol population Serious Adverse Event Total cholesterol Total cholesterol, high-density lipoprotein ratio Triglycerides |   |
| U.S. FDA
US
VLDL   | the U.S. Food and Drug Administration United States Very-low density lipoprotein  |   |

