Along with the fist supplement order shipped to the new subscriptions, participants will receive the baseline hearth health test kit from ImawareTM. Participants will be contacted 3 and 6 months after and they will be sent subsequent kits once the confirmed adherence to the supplement. The test kits will monitor blood lipid levels across a supplementation period (baseline, month 3 and month 6) thanks to a finger prick blood drawing system. The age, height, weight, gender, fasting total cholesterol, LDL-cholesterol, HDL-cholesterol, calculated VLDL-cholesterol, triglycerides, as well as hs-CRP inflammatory marker, and glucose and HbA1c as diabetes indicator of each participant will be recorded over the study period. **Qualitas Health** will receive the aggregated data of the participants only for statistical analyses at their headquarter in Houston and store it in the company share drive with access restricted to those involved in the study. There will be no cost incurred for this analytical assessment to the participant.

Results for the per intended-to-treat (ITT) population will be first tested for normality before any other test will be conducted and baseline data was compared against month 3 and month 6 data. Based on the distribution of data, either Welch two-sample unequal variance t-tests or Wilcoxon Ranks sum tests will be used to compare two-tailed differences between groups. Differences will be considered statistically significant at a p value < 0.05, but the thresholds for the significance of the 20 clinical outcomes were adjusted for multiple variables by the Bonferroni adjustment method which decrease the significance of p-value from <0.05, down to <0.0025. Intervention

effect will also test using an analysis of covariance model (ANCOVA) adjusting for baseline parameters.

[figure not shown]

Figure 1-1 Study design

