### 2.7. Analysis sets

### 2.7.1. Per protocol set (PPS)

The Per-Protocol Set (PPS) will consist of a subset of participants in the database who complete all 3 tests (baseline, month-3, and month-6 tests).

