### 2.7.2. Intention-To-Treat (ITT)

The Intention-To-Treat (ITT) will consist of a subset of participants in the database who complete at least 2 tests (baseline and month-3 test and/or month-6 test.

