### 3. Sample size calculation

Power and sample size calculation was performed on the primary outcome (triglycerides) using G\*Power 3.1 (Department of Psychology, University of Düsseldorf, Germany). Sample size calculation was based on a student t-test (two independent samples). Using an effect size of 0.5, and an allocation ratio N2/N1 of 1, the sample size was estimated to be 210 to achieve a power of 95%.

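### Removal for cholesterol medication makes missing month-6 values depend on measured values, and neither the unpaired test nor the planned analysis sets allow for it; the bias is of unknown size and direction, and probably small

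*SAP*

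**What the plan says.** SAP 2.10 (same rule in Protocol 10.6) states that "any participant that records out-of-range analytical levels will be referred to their GP". The GP may let the person carry on with the supplement, or the person is "placed on standard care of cholesterol-lowering medication (and removed from the trial"). No cut-off, marker or expected number is given.

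The sets are defined by tests completed. SAP 2.7.1 limits the per-protocol set to those "who complete all 3 tests (baseline, month-3, and month-6 tests"), and SAP 2.7.2 limits the ITT set to those who "complete at least 2 tests (baseline and month-3 test and/or month-6 test"). The SAP's abbreviation list contains "Full Analysis Set", but section 2.7 does not define one. SAP 2.8 says what happens to data when consent is withdrawn; it does not cover removal by the GP.

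For the comparison of baseline with months 3 and 6, SAP 1.1 (Study design) says "either Welch two-sample unequal variance t-tests or Wilcoxon Ranks sum tests will be used to compare two-tailed differences between groups". It adds an "analysis of covariance model (ANCOVA) adjusting for baseline parameters". SAP 3 sizes the study on a "student t-test (two independent samples). Using an effect size of 0.5".

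**The concern.** A participant with a high value is more likely to be medicated and so to have no month-6 result. The gap in the data is therefore not random, and with one arm there is no control group in which the same loss would show.

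Two features of the analysis let this reach the estimate. First, the test is unpaired, so the baseline mean and the month-6 mean can come from different people. Second, the sets treat removed people unevenly: someone removed after month 3 keeps a baseline in the ITT set, while someone removed after the baseline result disappears from both sets. The per-protocol set and any baseline-adjusted month-6 model lose both kinds. At stake is the month-6 change in triglycerides (primary) and in the cholesterol fractions.

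**Working it through.** **The plan's own figure.** A two-sample t-test with d = 0.5, 1:1 allocation, 95% power and two-sided alpha 0.05 (alpha is not stated in SAP 3) needs 105 per group, which is 210 in total (exact power 0.9501). SAP 3's 210 reproduces. In this trial, however, the two groups are the same people at two visits. With 210 values at each visit the unpaired standard error is sqrt(2/210) = 0.098 SD. At a between-visit correlation of 0.6, the paired one is sqrt(2 x 0.4/210) = 0.062 SD. The unpaired test is therefore conservative before any removal.

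**Who contributes what.** That month 6 is missing is inferred from the removal itself, and from kits being sent only once adherence is confirmed (SAP 1.1).

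| Removed after | Baseline in ITT | Month 6 | In PPS |
|---|---|---|---|
| baseline result | no | missing | no |
| month-3 result | yes | missing | no |

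**Assumptions (none in the documents).** Values are normal with SD 1, there is no true change, a share p lies above the cut-off, and a fraction g of those is removed. The common between-visit correlation is r. A negative shift is an apparent fall.

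**One trigger visit, unpaired ITT comparison.** The mean of the top share p is m = phi(z)/p. With q = p x g removed, those left have mean -qm/(1-q) at the trigger visit. Hence:

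- Month 3 triggers: shift = -r x qm/(1-q).
- Baseline triggers: shift = +(1-r) x qm/(1-q).

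For the top 20%, m = 0.280/0.20 = 1.40.

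- Half removed: q = 0.10 and qm/(1-q) = 0.140/0.90 = 0.156. Month 3 gives -0.078 (r = 0.5) and -0.109 (r = 0.7). Baseline gives +0.078 and +0.047. Simulation gave -0.077, -0.109, +0.077 and +0.046.
- All removed: q = 0.20 and qm/(1-q) = 0.280/0.80 = 0.35. Month 3 gives -0.175 and -0.245; baseline gives +0.175 and +0.105.

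**Both visits trigger (the plain reading of the rule).** The two effects partly cancel. Simulated unpaired ITT shifts in SD, 4,000 null trials of 210 per scenario:

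| r | Top share | 30% removed | 50% | 100% |
|---|---|---|---|---|
| 0.5 | 10% | +0.003 | +0.007 | +0.033 |
| 0.5 | 20% | +0.005 | +0.013 | +0.070 |
| 0.7 | 10% | -0.017 | -0.021 | -0.011 |
| 0.7 | 20% | -0.027 | -0.038 | -0.001 |

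A separate run with r up to 0.8, the top 10-30% and 30-50% removed reached about -0.086 (r = 0.8, top 30%, half removed). Against the planned 0.5, -0.09 is 18% and +0.07 is 14%. In the tabulated scenarios a false significant fall occurred in at most 0.6% of Welch tests at 0.05 and 0.03% at 0.0025 (= 0.05/20, the SAP's adjusted threshold), and a false rise in at most 6.1%.

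**Within-person tests on the planned sets.**

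- Completers-only paired test, both triggers, half removed: false rise in 6.8% to 16.2% (nominal 2.5%).
- Completers-only paired test, month 3 only: shift 0.00 with equal correlations, but about -0.03 SD if month 3 to month 6 correlates 0.7 and the other pairs 0.5 (top 20%, half removed).
- Mixed model on the 2.7.2 ITT set, both triggers, half removed: +0.03 to +0.08 SD.
- Mixed model on everyone with a baseline, with the endpoint itself as trigger: within 0.004 SD of zero in all 36 scenarios (r = 0.5 or 0.7, any trigger visit); two-sided rejection 4.1% to 5.7% at 0.05; standard error 0.054 to 0.093 SD.

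**Triglycerides when cholesterol is the trigger.** Assumed: triglyceride correlation 0.5 between visits, cholesterol 0.7, within-visit 0.5, top 20%, half removed, both visits.

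| Cross-visit triglyceride-cholesterol correlation | Planned unpaired test | Triglyceride-only mixed model |
|---|---|---|
| 0.45 | -0.046 | -0.050 |
| 0.30 | -0.006 | -0.013 |
| 0.15 | +0.035 | +0.024 |

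The triglyceride-only model is about as biased as the unpaired test here. Adding cholesterol at baseline and month 3 brings the shift back to zero.

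**The case against.** The strongest reply is that this hardly matters. With both visits triggering, false falls are rarer than the nominal 2.5%, the shifts are a fraction of 0.5 SD, and the GP may let people continue. The most extreme results (-0.25 SD with 78% false falls for month 3 only; +0.18 SD with 46% false rises for baseline only) need every out-of-range participant to be removed at one visit. That stands, and it is why this is a point to consider rather than a serious flaw.

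The trigger is also simplified. The rule covers any out-of-range level, SAP 2.12 lists eight markers, and low HDL, hs-CRP and glucose were not modelled. That stands too, and it makes the size less certain in both directions. The unpaired test would be the wrong choice even without removals; the same change of model deals with both.

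A reader might infer that the rule manufactures a benefit for the product. The documents do not support that: the sign depends on which visit triggers and on the correlations, and no document gives either. Nor can it be said that pairing always leaves a bias against the product; that is usual when baseline results trigger removal, but not when only month 3 does. A lipid drug started without the study's knowledge could be credited to the product. That is speculative, since the referral route already removes those it medicates.

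**Conclusion.** The gap is real: removal depends on measured values, the sets drop some of the recorded baselines, the test ignores that the values are paired, and no planned analysis allows for the reason a test is missing. The clinical rule itself is not in question.

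The size and direction of the bias cannot be known from the documents. The range of about -0.09 to +0.07 SD belongs to the points checked with both visits triggering (correlation 0.5 to 0.8, top 10-30% out of range, 30-100% of them removed, though not every combination). It is not a bound: the upper end came from removing all of the top 20%, and removing all of a larger share would pass it. Among the points checked, clearly larger shifts needed heavy removal at a single visit. For triglycerides the shift is probably smaller if cholesterol prompts removal; it was within 0.05 SD in the cases tabulated above.

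**What to change.** Leave the clinical rule as it is.

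1. Replace the Welch or rank-sum comparison with a within-person repeated-measures mixed model: visit as fixed effect, unstructured covariance, log scale for skewed markers, records linked by study number.
2. Fit it to everyone with a baseline value, including those with a baseline only, and use every value up to removal, including the one that led to referral. The undefined full analysis set could be defined this way. Do not fit it only to the 2.7.2 ITT set or rely on a completers-only paired test.
3. When the endpoint is not the marker that prompted referral, model it jointly with that marker's baseline and month-3 values.
4. Report the number removed, the trigger visit and their last values, so that readers can judge the size.
5. Optionally, ask about new lipid-lowering drugs at the month-3 and month-6 contacts already planned.

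The cost is SAP wording and a little more analysis. Rows by participant are already needed to form the sets and fit the ANCOVA, and Protocol 10.5 provides study numbers. If the laboratory's sheet in SAP 2.12 holds only group totals, a data request is needed. The estimate may move in either direction.

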### 2.11. Adverse events (AEs)

### **AE** summaries

AEs will be documented for participants which will be available at the time of analysis.

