10.1 Treatment Schedule

Study Stage	Specific Timing	Activity
Planning	N/A	Approval of protocol
2 Months		Independent peer-review

		Logistical arrangements	
		Recruitment	
Pre-Study	Upon approval and	Preliminary screening against inclusion and exclusion criteria	
·		Pre-study interview:	
1 Month	completion	 Information email and gain informed consent from the 	
	of recruitment	participant	
		 Enrolled participants purchase the product and receive the testing kits along with instruction regarding the study requirements. 	
Study	Baseline data collection	First test kit will be shipped to imaware	
Week 0-24	Trial Period	Participant takes product as instructed	
		Participant will receive and send the test kits on month 3 and 6	
		Participant completes end-trial blood test.	
		Participants exit email or phone interview to address adherence.	
Trial			
Months 0-6			
(Period begins at	Trial end interview		
, -			
trial week 2)			
End-Study			
Month 3			
Post-Study	N/A	Data verification and statistical analysis	
		Report drafting and approval	
		Study debrief and review	
*51		receive product will only occur after all inclusion criteria have	

^{*} Please note that enrolment in the trial to receive product will only occur after all inclusion criteria have been met.

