10.3. Risks and Discomforts

As in the case of taking any treatment, we cannot guarantee that participants will not experience any uncomfortable effects during this study. The treatment includes the following ingredients: Almega PL.

There are 4 reported causes of adverse effects of orally dosed supplements containing EPA reported on the TGA database. Specifically, diarrhoea, dry skin, enteritis infection (inflammation of the small intestine) and nephrolithiasis (kidney stones). These events are 4 out of several thousands of participants. A 2011 study using a similar EPA based product and involving 229 participants found the product to be well tolerated.

There is also a risk of discomfort that may be experienced because of the blood draws with finger prick. Blood sampling can cause pain, bleeding, bruising, and/or swelling at the site of needle penetration (risk less than 1 in 50). Fainting may occur (risk less than 1 in 100), and infection rarely occurs (risk less than 1 in 1000).

Should participants experience any of these or other mild adverse effects or have other concerns about the treatment, blood collection, or data collection please contact the investigators (24 hours a day). Our contact details are found in the Contacts section of this document and the 24-hour contact mobile number is also on the product label.

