## 4-Mar-2022

### 2.2. Data included in the analysis

The study data will be analyzed and reported based on all patient's data when all participants have completed at least 2 tests or discontinued the study (ITT population).

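### The SAP defines no safety set or AE denominator, so adverse events in people who start the product and stop early may be left out of the summary

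*SAP*

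**What the plan says.** SAP 2.11 consists of one sentence: "AEs will be documented for participants which will be available at the time of analysis". It gives no population, denominator or collection window.

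SAP 2.7 defines two sets. The per-protocol set is the "subset of participants in the database who complete all 3 tests (baseline, month-3, and month-6 tests". The set called ITT is the "subset of participants in the database who complete at least 2 tests (baseline and month-3 test and/or month-6 test". There is no set of everyone who took the product.

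Two further rules decide who can reach a second test. Under Study Design (Protocol 9, SAP 1.1), the month-3 and month-6 kits are sent only after the participant has confirmed adherence. Under SAP 2.6, a participant whose baseline kit is not mailed back or is lost has to be discontinued, because supplementation may already have begun.

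Other text points towards wider inclusion. SAP 2.2 says that reporting is "based on all patient's data when all participants have completed at least 2 tests or discontinued the study (ITT population". SAP 2.8, like Protocol 10.4, says: "If participants withdraw their consent, all data collected up until that time will be used in the analysis of the data".

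On collection, Protocol 9 describes a follow-up email to evaluate adherence, and Protocol 10.1 lists "Participants exit email or phone interview to address adherence". For side effects, Protocol 10.3 asks participants to make contact themselves: "please contact the investigators (24 hours a day".

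**The concern.** A safety summary should cover everyone exposed. Here the people whose events matter most, those who started the product and gave it up, are the ones least likely to have a second test. The events that the protocol reports from the previous placebo-controlled trial (nausea, abdominal cramping, diarrhoea; Protocol 8.3.1) are of a kind that could lead someone to stop. If the AE summary follows either defined set, or follows who is still reachable when the data are analysed, the AE rate would tend to err in the product's favour. With a single arm, there is no comparison group in which under-reporting might show. With no stated denominator, a reader could not interpret the published rate.

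**Working it through.** **The plan's own figures.** The documents state no AE rate, dropout rate or safety denominator, so there is no AE figure to reproduce. The one calculated number in the SAP, N = 210 in section 3, does reproduce: two-sided t-test, alpha 0.05, effect size 0.5, ratio 1, giving 105 per group with power 95.01%. It is not at issue and serves below only as a head count.

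**Who is covered by which rule.**

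| Participant who started the product | Per-protocol set (2.7.1) | ITT set (2.7.2) | Withdrawal rule (2.8) | Data included (2.2) |
|---|---|---|---|---|
| Stops before month 3 and withdraws consent | No | No | Yes, for data already collected | Has discontinued, but the population is labelled ITT |
| Stops before month 3 and goes silent | No | No | Not expressly | As above, if counted as discontinued |
| No baseline result, discontinued under 2.6 | No | No | Not expressly | As above |
| Removed under 2.10 before a second test | No | No | Not expressly | As above |
| Stops after returning the month-3 test | No | Yes | Yes, if consent is withdrawn | Yes |

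The first four rows are people exposed to the product who belong to neither set. Section 2.2 would admit them by speaking of all patients' data, but it calls that population ITT, and 2.7.2 limits ITT to people with two tests.

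**The two readings of 2.11.**

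- If *available* describes the participants, people who left early are outside the rule.
- If it describes the AEs, an event that an early stopper has already reported is kept. An event that nobody asked about is still missing, and there is still no denominator.

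**Illustration of size, on assumed rates only.** Let d be the share with no second test, a_in the AE risk in people with two tests, and a_out the risk in the rest. Suppose that the summary is limited to people with two tests, that all their events are captured, and that no others are.

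- True rate = (1 − d) × a_in + d × a_out
- Share of participants with an AE who are missed = d × a_out / true rate

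Assume d = 10% to 40%. Then 21 to 84 of 210 participants are outside both sets (20 to 80 of 200; 30 to 120 of 300, the ends of the enrolment range).

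- Equal risk, a_in = a_out = 5%: the true rate is 5%. Missed share: 0.10 × 5 / 5 = 10%, up to 0.40 × 5 / 5 = 40%. The rate stays at 5% if the denominator is also limited to people with two tests. If everyone is in the denominator, it falls to 0.9 × 5% = 4.5%, or 0.6 × 5% = 3%.
- Higher risk in stoppers, a_in = 5%, a_out = 15%: the true rate is 0.9 × 5% + 0.1 × 15% = 6%, up to 0.6 × 5% + 0.4 × 15% = 9%, against a reported 5% among people with two tests. Missed share: 1.5 / 6 = 25%, up to 6 / 9 = 67%.

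If events already on file are kept, as 2.2 and 2.8 suggest, the missed share is smaller. It is zero if every early stopper's event was reported.

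**The case against.** The strongest reply is that 2.11 excludes nobody. It does not say that AEs are documented *only* for some people, and it names neither set. The sets are defined by test kits, while AE reports arrive through contact with the investigators, which needs no kit. Sections 2.2 and 2.8 say that data from people who discontinue or withdraw are used. Protocol 10.2 and SAP 2.5 call the contacts clinical interviews and require an exit interview, so AEs may be raised there. AEs are also neither a primary nor a secondary endpoint.

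Much of this stands. A reader might infer that early stoppers' events are certainly lost, or that both readings of 2.11 lose the same events. The documents support neither inference: under the second reading, an event reported before leaving is retained. Nor is it shown that the contacts deal with adherence alone; adherence is simply the only content stated.

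The reply does not remove the problem. Section 2.8 covers withdrawn consent and data already collected. It does not expressly reach people who go silent or who are discontinued or removed, and it cannot supply an event that was never asked about. Section 2.2 conflicts with 2.7.2 over what ITT means. No text assures that early stoppers' events are counted.

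**Conclusion.** The point holds as a risk of omission, not as a demonstrated loss. There is no safety set and no AE denominator. Both defined sets require two tests, and access to a second test depends on confirmed adherence. SAP 2.11 and 2.7.2 are in tension with 2.2 and 2.8. AE capture, as described, is passive, and that affects people who stay as well as those who leave.

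The likely direction, if early stoppers are left out, is an understated AE rate. This rests on the assumption that people who stop early have events more often than those who stay, or on a denominator that includes people whose events are not counted. A reader might want to attach a percentage to the loss. The documents do not allow it: the 10% to 40% and 25% to 67% above come entirely from assumed rates and from full capture on one side and none on the other. No planned efficacy result depends on this, but the AE rate could not be interpreted as the plan stands, and the change should be made.

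**What to change.** Replace the sentence in SAP 2.11 with a safety set of all participants who started the product, whatever kits they returned, including those who withdrew, were discontinued or were removed. Use that number as the AE denominator. Where intake is unknown, include everyone who was shipped the product and is not confirmed as never having taken it.

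Reconcile SAP 2.2, 2.7.2 and 2.8 with this, so that the label ITT has one meaning and the treatment of data from people who stop is the same throughout.

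Add one AE question and the reason for stopping to the planned month-3, month-6 and exit contacts, and put them also to participants who report having stopped. The documents describe no separate withdrawal contact, so the change should not depend on one. Report next to the AE rate how many of the safety set answered the question.

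The cost is a rewritten SAP sentence with matching edits, one AE question plus the reason for stopping in contacts already planned (a change to data collection, so the protocol text must match), and an AE rate that may be slightly less favourable.
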